### 1.2.1 Flow chart

The flow chart of the trial assessments by visits are shown in Figure 2.

Type of document Document ID	INTERNAL USE	Date: Version:	11-Aug-2022 4.0	Status: Page:	Final 21 of 79	ALK
Boodment IB		Version.	4.0	r age.	79	

#### Figure 2 Flow chart

Visit ID:	V1	TC1	V2	TC2	V3	V4	TC3, 4	V5	TC5, 6, 7	V6	TC8, 9, 10	V7	TC11, 12, 13	V8	TC14, 15, 16	V9	TC17, 18, 19	V10 	TC20 	V11 	TC21	UN
Visit:	Screen ing	Reten- tion	Base- line	Mid base- line call	Ran- domi- sation	Visit 4		Visit 5		Visit 6		Visit 7		Visit 8		Visit 9		Visit 10		Final visit	Follow -up	Un- sche- duled visit
Time  from randomisation (IMP initiation) for all visits and TCs, except for visit 11 (actual date of visit)	Max 12 wk before V3		- 3 wk - 7 d	- 2 wk ± 2 d	-	+ 4 wk + 7 d	+ 2m ±2d + 3m ±2d	+ 4m ± 7 d	+ 5m ±2d + 6m ±2d + 7m ±2d	+ 8m ± 7 d	+9m ±2d +10m ±2d +11m ±2d	+ 12m ± 7 d	+13m ±2d +14m ±2d +15m ±2d	+ 16m ± 7 d	+17m ±2d +18m ±2d +19m ±2d	+ 20m ± 7 d	+21m ±2d +22m ±2d +23m ±2d	+ 24m ± 7 d	2 wk prior to V11 ± 2 d	30 Apr ± 7 d	+ 2 wk from V11 + 7 d	
Informed consent and assent 	x																					
Demography	х																					
Medical history incl. evaluate previous asthma exacerbations	х																					
SPT 	х		(X)																			
Review of in-/exclusion criteria	х		х		х																	
Randomisation					х																	
Physical examination 	х																			х		(X)

<sup>1 Visit 10 is not applicable for subjects randomised in cohort 1 after 31-Mar-2018; for subjects randomised in cohort 2 after 31-Mar-2019, for subjects randomised in cohort 3 after 31-Mar-2020 and for subjects randomised in cohort 4 after 31-Mar-2022, if applicable.

<sup>2 TC20 performed 2 weeks prior to final visit.

<sup>3 Visit 11 will take place on 30-Apr-2020  $\pm$  7 days for cohort 1, 30-Apr-2021  $\pm$  7 days for cohort 2, 30-Apr-2022  $\pm$  7 days for cohort 3.

<sup>4 One month (m) is considered 30 days.

<sup>5 Obtain written informed consent for the trial, storage of serum samples in the ALK Research Biobank, and for pharmacogenetics testing, before any other trial procedures are performed.

<sup>6 If medication that could interfere with the SPT has not been washed out and the positive control is <3 mm for subjects in Europe or < 5 mm for subjects in North America, the SPT must be repeated after the interfering medication has been washed out.

 Oropharyngeal examination is included in physical examination

															Ũ	79						
Visit ID:	V1	TC1	V2	TC2	V3	V4	TC3, 4	V5	TC5, 6, 7	V6	TC8, 9, 10	V7	TC11, 12, 13	V 8	TC14, 15, 16	V9	TC17, 18, 19	V10 	TC20 	V11 	TC21	UN
Oropharyngeal Examination			х		X 	х		х		х		х		х		х		х				(X)
Height and weight 	х		х		х	Х		х		х		х		х		х		х		х		х
Vital signs	х		х		х	Х		х		х		х		х		х		х		х		(X)
FEV1 	х		х		х	х		х		х		х		х		х		х		х		х
Urine pregnancy test, if applicable 	x		х		х	х		x		х		х		x		х		х		х		(X)
Blood and urine samples for safety laboratory assessments	х											x								x		(X)
Blood sample for specific IgE 	x	(X) 																				(X)
Recording of asthma exacerbations 	x	х	х	x	х	х	х	x	х	х	х	х	х	х	х	х	х	х	х	х	х	х
Assess and record AEs	х	Х	х	х	х	Х	Х	х	х	Х	Х	х	Х	х	х	х	х	х	Х	х	X 	х
Assess eosinophilic oesophagitis	x		x		х	х		x		х		x		x		х		х		x		(X)
Record concomitant medication	x	x	x	x	х	х	х	x	x	х	х	x	x	x	х	х	x	x	x	x	x	х
					х	х	х	х	x	х	х	х	х	х	х	х	х	х	х	х		х

Date:

Version:

11-Aug-2022

4.0

Status:

Page:

Final 22 of Type of document

Document ID

INTERNAL USE

<sup>8 Oropharyngeal examinations will be done before and 60 mins after IMP administration at visit 3

<sup>9 If applicable, adjust the Asthma Action Plan and Local and Systemic Allergic Reaction Emergency Plan

<sup>10 Measure  $FEV_1$  and calculate the % of predicted  $FEV_1$  after 6 hours of SABA.

<sup>11 For female subjects of childbearing potential, additional urine pregnancy tests should be performed during the trial, if a menstrual period is missed.  IgE against *D pteronyssinus, D farinae, Cladosporium herbarum* and *Blattella germanica* 

<sup>13 Inform subjects of continued participation in trial depending on the blood sample for specific IgE against *D. pteronyssinus* and *D. farinae* 

<sup>14 In case of an asthma exacerbation the subject should be called in for an unscheduled visit.

<sup>15 If an AE was ongoing at the previous visit, if a new AE is identified at the telephone contact or if 1 of the safety laboratory parameters measured at the previous visit showed a clinically significant abnormality, the subject could be asked to return to the trial site.

Type of document Document ID						INTER	NAL US	E		Date Vers	: ion:	11-Au 4.0	g-2022		Statu Page	IS: ):	Final 23 of 79			_K		
			.			.						I					 -					I
Visit ID:	V1	TC1	V2	TC2	V3	V4	TC3, 4	V5	TC5, 6, 7	V6	TC8, 9, 10	V7	TC11, 12, 13	V8	TC14, 15, 16	V9	TC17, 18, 19	V10 	TC20 	V11 	TC21	UN
					х	х	х	х	х	х	х	х	х	х	х	х	х	х	х	х		х
Issue and review Asthma Action Plan 			х																			
Issue and review Local and Systemic Allergic Reaction Emergency Plan 			x		x																	
ACQ or ACQ-IA					х			х		х		х		х		х		х		х		х
18					х			х		х				х				х		х		х
					х					х										х		Х
19			Х					х				х				х				х		х
			Х		х			х		х		х		х		х		х		х		Х
Global Evaluation (asthma and AR)																				х		
Blood sample for Immunological assessments					x							x								x		(X)
Blood sample for pharmacogenetics					x															x		
Biobank blood and urine sample					x							х								x		
Dispense IMP					х			х		х		х		х		х		х				(X)

19

 <sup>16 Dispense Peak Expiratory Flow (PEF) meters.
  Instruct in the use of rescue medication for severe allergic reaction, in countries where it is a regulatory requirement. 18

																	79					
Visit ID:	V1	TC1	V2	TC2	V3	V4	TC3, 4	V5	TC5, 6, 7	V6	TC8, 9, 10	V7	TC11, 12, 13	V8	TC14, 15, 16	V9	TC17, 18, 19	V10 	TC20 	V11 	TC21	UN
Intake of IMP at clinic					X20																	(X)
Dispense asthma and rhinoconjunctivitis rescue medication21			x		x	x		x		x		x		x		x		x				(X)
Evaluate inhalation technique			х									х										
Collect IMP, perform compliance check and drug accountability								x		x		x		x		x		x		x		
Collect rescue medicatior as applicable and perform drug accountability	ו				x	x		x		х		х		х		x		x		х		
Show and discuss Trial video			х																			
Issue and instruct in the use of an eDiary			х																			
Instruct in the recording of prespecified symptoms in eDiary	5				x																	
Review eDiary and record solicited AEs in eCRF						x																
Activate eDiary for the next period			х		х	х		х		х		х		х		х		х				
Daily eDiary recording					-3 wk	-4 wk22		-3 wk		-3 wk		-3 wk		-3 wk		-3 wk		-3 wk		-3 wk		
Check eDiary compliance					х	х		х		х		х		х		х		х		х		

Date:

Version:

INTERNAL USE

11-Aug-2022

4.0

Final 24 of

Status:

Page:

Type of document

Document ID

<sup>20 Perform oropharyngeal examination before and 60 mins after IMP intake. For subjects with severe oral inflammation (e.g. oral lichen planus, mouth ulcers or thrush), oral wounds or following oral surgery, including dental extraction, or following tooth loss, initiation of IMP treatment should be postponed until the oral cavity has healed.
 Dispense rescue medication for severe allergic reaction (adrenaline/epinephrine) in countries where this is applicable.

<sup>22 eDiary recording of prespecified symptoms

Type of document Document ID						INTERI	NAL US	Date: USE Version:		11-Au 4.0	ıg-2022		Status: Page:		Final 25 of 79	ALK						
Visit ID:	V1	TC1	V2	TC2	V3	V4	TC3, 4	V5	TC5, 6, 7	V6	TC8, 9, 10	V7	TC11, 12, 13	V8	TC14, 15, 16	V9	TC17, 18, 19	V10 	TC20 	V11 	TC21	UN
Collect eDiary																				х		

Type of document	Date:	11-Aug-2022	
Document ID	Version:	4.0	
	Status:	Final	
INTERNAL USE	Page:	26 of 79	

### 1.2.2 Visit windows

See the flow chart in Figure 2.

### 1.2.3 Randomisation

The randomisation list has been generated by a trial-independent statistician and will not be accessible to trial personnel involved in the conduct of the trial, until the database has been locked.

At least 45% of the subjects will be 5-11 years of age at the time of randomisation in accordance with the recommendation of EMA/PDCO standard paediatric investigation plan for allergen products for specific immunotherapy **(EMA and PDCO 2015)**. No other stratification will be used in this trial.

When a subject is randomised, a unique number is assigned for the first dispensing of IMP.

## **2** STATISTICAL HYPOTHESES

### 2.1 Multiplicity adjustment

The primary and key secondary endpoints will be controlled for multiplicity to ensure a maximum overall type I error rate of 5% in the hypothesis testing of these endpoints. The control for multiplicity is done by hierarchical testing, pre-specifying the order of the hypothesis to be tested. For all endpoints the null hypothesis to be tested is the hypothesis of no difference between treatment groups.

The order of hypothesis to be tested is:

- 1. Superiority testing of the HDM SLIT-tablet over placebo with respect to the rate of clinically relevant asthma exacerbations during the efficacy evaluation period (primary objective, section 1.1.1). The primary estimand will be used.
- 2. Superiority testing of the HDM SLIT-tablet over placebo with respect to proportions of days with nocturnal awakenings due to asthma which require SABA use during the 14 days eDiary period recorded every 4 months after randomisation (first key secondary objective, section **1.1.2**).
- 3. Superiority testing of the HDM SLIT-tablet over placebo with respect to the proportions of days with SABA use during the 14 days eDiary recording every 4 months after randomisation (second key secondary objective, section **1.1.2**).
- 4. Superiority testing of the HDM SLIT-tablet over placebo with respect to the percentage predicted FEV1 assessed every 4 months after randomisation (third key secondary objective, section **1.1.2**).

All hypotheses in the hierarchy are tested on a 5% significance level, i.e. significance is obtained when a p-value is below 5%. If the first hypothesis is statistically significant at the 5% level, i.e. the null hypothesis of no difference is rejected, then the second hypothesis is tested, and so forth. A hypothesis is only tested if all previously tested hypothesis were statistically significant at the 5% level, i.e. all previous null hypotheses were rejected.

Type of document Document ID	Date: Version: Status:	11-Aug-2022 4.0 Final		<
INTERNAL USE	Page:	27 of 79		

### 3 ANALYSIS SETS

For the purposes of analysis, the following participant analysis sets are defined:

Analysis set	Description
FAS	The FAS consists of all randomised subjects, who received at least 1 dose of IMP. Subjects will be analysed as randomised, i.e. according to their randomised assignment of treatment.
SAF	The SAF consists of all randomised subjects, who received at least 1 dose of IMP. Subjects will be analysed as treated, i.e. according to the treatment they actually received.
PP	The PP will consist of all subjects in FAS without protocol deviations, which may substantially affect the primary endpoint. Subjects will be analysed as randomised, i.e. according to their randomised assignment of treatment.

Before database lock, a list will be made that defines which subjects in FAS are not included in PP and the reason for this. The criteria for not including subjects in PP are the following:

- 1. Violation of the inclusion/exclusion criteria that may potentially impact the primary endpoint
- 2. Use of prohibited medication close to or during the efficacy evaluation period (period 4) that may potentially impact the primary endpoint
- 3. Treatment compliance in the entire trial. Subjects with a treatment compliance below 80% are not included in the PP
- 4. Efficacy compliance. Subjects with less than 6 months of efficacy assessment in period 4 are not included in the PP

The list of subjects in PP is found in Appendix 4 section 7.4.

The FAS will be used for baseline tables and efficacy output and the SAF will be used for safety tables and listings. The PP will be used for a supportive analysis of the primary endpoint.

DPS	Description
DPS1	
 
Subjects who are treated in period 4 will be included.
 
Post-discontinuation data will not be included.
 

DPS2	
 
Only subjects who complete treatment in period 4 will be included.
 

The following data point sets are defined:

FAS and DPS1 are used to estimate the primary estimand for the primary endpoint and the primary estimand for the key secondary endpoints.

FAS and DPS2 are used to estimate the secondary estimand for the primary endpoint.

Type of document	Date:	11-Aug-2022	
Document ID	Version:	4.0	
	Status:	Final	
INTERNAL USE	Page:	28 of 79	

In addition, to investigate the impact of covid-19 (see section **3.2**), the following observation periods are defined:

OP	Description
OP1	• The time period is from the start of the trial and until March 20, 2020, both dates included
OP2	• The time period is from March 20, 2020 (excluded) until the end of the trial

### 3.1 Issue at site 613

In Sep-2018 the CRO discovered that 2 subjects at the site had been enrolled in 2 different trials for 2 different sponsors at the same time. Evaluation from the CRO medical monitor review showed that subjects' safety was not affected. All 9 subjects at the site were discontinued from the trial in Nov-2018 and the site was terminated in Mar-2019.

Thus, efficacy data from site 613 are neither included in the PP, nor in the FAS. However, safety data from site 613 are included in the SAF.

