5.1 Discontinuation from IMP treatment

Subjects must be discontinued from IMP treatment and should continue in the trial for safety assessments only under the following circumstances:

- If the subject experiences 2 severe asthma exacerbations within a 12 consecutive months period
- If the subject is hospitalised due to asthma requiring treatment with systemic corticosteroids
- The subject experiences severe or persistent symptoms of oesophagitis
- If the subject becomes pregnant
- If, in the investigator's opinion, continuation with IMP treatment would be detrimental to the subject's well-being

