15.3 Analysis data sets

The total analysis set

The total analysis set comprises all subjects who entered the trial. This analysis set includes screening failures. The total population will be used for listing reasons for screening failures and AEs before randomisation.

The full analysis set

The full analysis set (FAS) comprises all randomised subjects who received at least 1 dose of IMP. This analysis set will be the primary set for all efficacy analyses. The FAS will be used for all baseline/demography tables and efficacy tables and subject listings.

The per protocol analysis set

The per protocol (PP) analysis set comprises subjects without protocol deviations that may substantially affect the primary endpoint.

Before data base lock, a list will be made that defines which subjects are excluded from the PP analysis set and the reason for exclusion. The criterias for exclusion will be based on procotol deviations such as:

- 1. Violation of the inclusion/exclusion criteria
- 2. Use of prohibited medication close to or during the efficacy evaluation period (period 4)
- 3. IMP compliance in the entire trial. Subjects with a compliance below 80% are excluded from the PP analysis set
- 4. Diary compliance. Subjects with less than 6 months of efficacy assessment in period 4 are excluded from the PP analysis set

The PP analysis set will be used for a supportive analysis of the primary endpoint.

The safety analysis set

The safety analysis set (SAF) will be used for safety analyses. The SAF will include all randomised subjects who received at least 1 dose of IMP. Subjects will be included in the treatment group corresponding to the IMP they actually received during the trial. SAF will be used for safety tables and listings.

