### 4.2.1 Definition of endpoint

The primary endpoint of the trial is the annualised rate of clinically relevant asthma exacerbations calculated as the number of exacerbation events per subject year during the efficacy evaluation period (period 4).

Note that period 4 begins on September 1st for all subjects and lasts until the end of trial or discontinuation of IMP.

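### PP criterion 4 removes subjects whose short time in period 4 results from an IMP stop that the protocol itself requires after severe exacerbations, so the supportive analysis can understate a real effect

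*SAP*

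**What the plan says.** SAP section 3 defines the set as follows: "The PP will consist of all subjects in FAS without protocol deviations, which may substantially affect the primary endpoint". Its fourth criterion is "Subjects with less than 6 months of efficacy assessment in period 4 are not included in the PP". Protocol section 15.3 has the same rule: "Subjects with less than 6 months of efficacy assessment in period 4 are excluded from the PP analysis set". The protocol labels it diary compliance and the SAP labels it efficacy compliance. Neither distinguishes between reasons for the short time. The role of the set is limited: "The PP will be used for a supportive analysis of the primary endpoint".

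Period 4 "lasts until the end of trial or discontinuation of IMP" (SAP section 4.2.1), and SAP section 7.1.1.2 counts its length up to the last IMP intake.

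Protocol section 5.1 opens its list with "Subjects must be discontinued from IMP treatment and should continue in the trial for safety assessments only under the following circumstances". Two of the circumstances are "If the subject experiences 2 severe asthma exacerbations within a 12 consecutive months period" and "If the subject is hospitalised due to asthma requiring treatment with systemic corticosteroids".

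SAP section 7.1.1.1 makes every severe exacerbation a clinically relevant one as well, so severe exacerbations in period 4 are primary-endpoint events. The PP row of SAP Table 1 uses DPS1 and lists period 4 discontinuations as included as observed. SAP section 4.2.5 says that the PP analysis handles intercurrent events as the primary estimand does.

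**The concern.** A subject who reaches a trigger between 1 September and the end of February of the first efficacy season has deviated from nothing. The stop under section 5.1 is compliance. It nevertheless leaves less than 6 months in period 4, so criterion 4 removes the subject and every period 4 event counted up to then. Membership of the supportive set therefore depends partly on the outcome being analysed.

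If the tablet works, placebo subjects reach the triggers more often, so more high-rate subjects are removed from placebo than from active. The PP rate ratio then moves towards 1. A modest attenuation in a supportive analysis can be misread as disagreement with the primary result.

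**Working it through.** **1. Reading the rules together.** Short time in period 4 leads to removal from PP (criterion 4). The time is short when IMP stops early (SAP 4.2.1, 7.1.1.2). IMP must stop after the triggers in protocol 5.1. Three limits apply:
- ICS doubling alone never triggers a stop.
- Severe events in period 3 count towards the 12-month window, so a single severe event in period 4 can be enough.
- The hospitalisation trigger has no minimum duration, whereas the endpoint asks for more than 12 hours. A short admission could therefore be a trigger without being an endpoint event.

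**2. The plan's own figure.** Inputs from protocol 15.1: 0.64 events per 24 weeks, 86 weeks, 30% reduction, k = 0.7, 90% power, two-sided 5%. Then μ1 = 0.64/24 × 86 = 2.293 and μ2 = 0.7 × 2.293 = 1.605.

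N = ((1.2816 + 1.9600)/ln(1/0.7))² × ((2.293 + 1.605)/(2.293 × 1.605) + 1.4) = 82.6 × 2.459 = 203.1, against 202 in Table 13. This figure is not in dispute; the simulation below starts from the same inputs.

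**3. Simulation of the criterion.** Set-up: 200,000 subjects per arm, gamma-frailty Poisson events with k = 0.7, true RR 0.70, 4 to 10 months in period 3 (uniform), 608 days in period 4, IMP stopped by the two triggers only. The model is negative binomial with a log-time offset. The severe share of events and the hospitalised share of severe events are assumptions, because the documents do not give them. The placebo rate of 0.5 is also assumed. Removal is a percentage of subjects who entered period 4.

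| Placebo rate/year | Severe / hospitalised | Removed, placebo / active | RR without criterion 4 | RR with it | Shift |
|---|---|---|---|---|---|
| 1.4 | 25% / 0% | 4.4% / 2.6% | 0.716 | 0.732 | +0.016 |
| 1.4 | 25% / 10% | 5.3% / 3.3% | 0.711 | 0.727 | +0.016 |
| 1.4 | 50% / 0% | 11.2% / 7.2% | 0.727 | 0.766 | +0.039 |
| 1.4 | 50% / 10% | 12.1% / 8.0% | 0.731 | 0.770 | +0.039 |
| 1.4 | 75% / 10% | 17.9% / 12.7% | 0.746 | 0.800 | +0.054 |
| 1.4 | 100% / 10% | 22.9% / 16.9% | 0.765 | 0.840 | +0.075 |
| 0.5 | 25% / 0% | 0.8% / 0.4% | 0.705 | 0.711 | +0.006 |
| 0.5 | 25% / 10% | 1.2% / 0.8% | 0.698 | 0.703 | +0.005 |
| 0.5 | 50% / 0% | 2.7% / 1.5% | 0.704 | 0.718 | +0.014 |
| 0.5 | 50% / 10% | 3.4% / 2.1% | 0.707 | 0.722 | +0.015 |
| 0.5 | 75% / 10% | 5.8% / 3.6% | 0.714 | 0.743 | +0.029 |
| 0.5 | 100% / 10% | 8.3% / 5.3% | 0.727 | 0.768 | +0.041 |

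With a true RR of 1.0 and the same settings, the fitted RR with the criterion is 0.997 to 1.006.

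**4. Which rates are plausible.** SAP 5.1 reports 81% power at 900 subjects, and protocol 15.2.1 assumes RR = 0.7. In the reassessment formula, ((0.878 + 1.960)/0.3567)² = 63.3 and 450/63.3 = 7.11. Assume 3% drop-out before period 4, 608 days and k = 0.7. Then 7.11 × 0.97 − 1.4 = 5.50, and the pooled rate is 1.7²/(2 × 0.7 × 1.666 × 5.50) = 0.225. The placebo rate is 0.225/0.85 = 0.27 per year. With 10% drop-out and 540 days it is 0.33. With k = 1.5 the two figures are 0.37 and 0.48. Rates of 0.6 or more need k of roughly 2 or above.

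**5. Adding unrelated stopping.** Further simulations assumed 12% per year unrelated stopping, 50–80% of events severe and 10–15% of severe events hospitalised.
- At placebo rates of 0.25 to 0.4, stops under section 5.1 remove 1–5% of placebo and 1–3% of active subjects, and the RR shift is +0.01 to +0.04.
- At 0.35 to 0.5, the shift is 0.01 to 0.05.
- At 0.6 to 1.4 with k 0.7–1.5, criterion 4 removes 9–14% of placebo and 8–11% of active subjects, and the shift is +0.015 to +0.057. Unrelated stopping alone accounts for about 1 − exp(−0.12 × 0.5) = 5.8% per arm, so much of that removal has nothing to do with the outcome.
- Exempting only the stops required by section 5.1 brought the RR to within 0.003 of the fit without the criterion in every scenario examined.

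**The case against.** The strongest reply is that nothing decisive rests on this set. The hierarchy in SAP 2.1 tests the primary estimand on FAS/DPS1, which keeps every subject treated in period 4, including early mandated stops. Sensitivity analysis 2 addresses period 4 discontinuation separately, and the SAP already requires a list of PP exclusions with reasons. A minimum-exposure rule in a PP set is common and was prespecified. All of this stands, and it limits the importance of the point.

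The shift is also small against the precision. The reassessment implies SE(log RR) of about 0.3567/2.838 = 0.126 at 450 per arm, or 0.126 × √(900/533) = 0.16 for the 533 randomised. The largest shift at rate 0.5, from 0.727 to 0.768, is ln(0.768/0.727) = 0.055, about a third of that.

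Two stronger readings are tempting:
- A reader might infer that the PP analysis cannot support the primary result. That does not follow. The pull is towards no effect and is absent under the null, so a PP analysis that still shows benefit does lend support.
- A reader might infer that the log-time offset makes the analysis unbiased once the criterion is dropped. It does not. The offset handles unequal exposure, not informative stopping: without the criterion the fitted RR at rate 1.4 is still 0.71–0.77 against a true 0.70.

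SAP 1.1.9.3 says that only 3 subjects stopped treatment without withdrawing from the trial at that time. This may hint at few mandated stops, but it does not bound them, because those subjects could also have withdrawn.

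What survives is the internal conflict: a rule meant to remove deviations removes compliant subjects because of their endpoint events, against the handling stated in Table 1 and section 4.2.5.

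**Conclusion.** The point holds as an inconsistency in the supportive analysis that should be corrected. The confirmatory analysis is untouched. With a true RR of 0.70, criterion 4 moves the PP ratio towards 1 by roughly 0.00 to 0.07, reaching 0.075 only if every event is severe. At the lower rates suggested by the reassessment under moderate dispersion, the shift is about 0.00 to 0.05. With no effect it adds no bias. The practical risk is a PP result that looks discordant when it is not.

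The sizes are illustrative. They rest on assumed severe and hospitalised shares, assumed unrelated stopping and an assumed placebo rate. The PP list in Appendix 4 is not in the text available here, so the actual number of subjects affected cannot be stated. The sponsor can count them from blinded data.

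**What to change.** Before unblinding, reword criterion 4 in SAP section 3 so that it covers only short follow-up not caused by an IMP stop required by protocol section 5.1. Record the departure from protocol 15.3 in SAP 4.8 and re-issue the PP list in Appendix 4. At minimum, report the PP analysis with and without criterion 4, with exclusions by arm and reason. Describe the revised analysis as matching the primary analysis's handling of discontinuation, not as unbiased.

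The cost is a sentence or two and a re-issued list. The downside is that a few subjects with short exposure stay in the PP set. No clinical stopping rule changes.
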